complete response is defined as the time between the date of first documented response of CR_{MRD} - to the date of the first documented relapse per ELN recommendations or death due to any cause, whichever occurs first.

The CR rate from Group 2 Subgroup C will be evaluated in the context of results from an ongoing retrospective study of AML patients who are similar to the inclusion/exclusion criteria of Group 2 Subgroup C patients. Any comparison of Group 2 data to results from the retrospective study will be described in a separate SAP.

Censoring rules for DOCR are provided in Table 10.

Table 10: Censoring Scheme for Primary Definition of DOCR

Situation	Date of Event or Censoring	Outcome
Relapse per ELN recommendations	Date of first relapse	Event
Death without relapse	Date of death	Event
No relapse and no death	Date of last evaluable disease assessment	Censored
New anti-cancer therapy received without relapse reported prior to or on the same day as disease assessment	Date of last evaluable disease assessment on or prior to the date of initiation of subsequent therapy	Censored
Two or more consecutive missed scheduled disease assessments	Date of last evaluable disease assessment prior to the missed disease assessments	Censored

Abbreviations: AML=acute myeloid leukemia; RFS=relapse-free survival

Relapse includes either hematologic and/or molecular relapse as defined in Table 6 at any disease assessment.

The CR rate and the corresponding 95% exact CI will be calculated. The DOCR will be estimated using the KM product limit method. The KM estimate of the median DOCR and the DOCR rates at milestone timepoints will be reported along with the two-sided 95% CI.

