Statistical significance testing will be two-sided and performed using $\alpha=0.05$. P-values will be reported for all statistical tests, rounded to four decimal places. P-values less than 0.0001 will be displayed as “<0.0001”; p-values greater than 0.9999 will be displayed as “>0.9999”.

7.1.2 *Summarization by Visit*

Data summarized by study visit will be based on the nominal, scheduled visit label as reported on the eCRF. Data collected at unscheduled visits will not be included in by-visit summaries, but will be considered when endpoint derivations potentially include multiple visits (eg, determination of baseline value, determination of worst post-baseline value, etc.). All data will be included in patient listings.

All efficacy data collected at unscheduled visits will be included in the derivation of efficacy endpoints.

7.1.3 *Data Handling Rules*

Unless otherwise noted, values reported as greater than or less than some quantifiable limit (eg, “< 1.0”) will be summarized with the sign suppressed in summary tables and figures, using the numeric value reported. Data will display on patient listings to include the sign.

7.1.4 **Standard Calculations**

Where appropriate, the calculated study day of each assessment or event will be presented with the assessment or event date on patient data listings, where study day will be determined as:

- The assessment/event date minus the date of first dose of MT-401 for patients enrolled in Cohorts I-V or Group 2
- The assessment/event date minus the date of randomization for all patients randomized in Group 1.

Other variables requiring calculations will be derived using the following formulas:

- **Days:** A duration between two dates expressed in days will be calculated as: later date – earlier date + 1
- **Months:** A duration expressed in months will be calculated by dividing the duration in days by (365.25 / 12);
- **Years:** A duration expressed in years will be calculated by dividing the duration in days by 365.25;
- **Change from Baseline:** Change from baseline will be calculated as the post-baseline value minus the baseline value;
- **Percentage Change from Baseline:** Percentage change from baseline will be calculated as the change from baseline divided by the baseline value, multiplied by 100.

7.1.5 **Definitions**

Standard definitions include:

- Actual follow-up time: last date known alive or death date – date of first dose of MT-401 (or date of randomization for Group 1 patient) + 1

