The primary analysis of RFS will be performed when 90 RFS events have been observed. RFS curves will be estimated using the Kaplan-Meier (KM) product limit method. The KM estimate of the median, 25th and 75th percentiles will be reported, and their corresponding 95% CIs will be computed. KM estimates of RFS rates at milestone time points (ie, 3 month intervals) will be reported along with two-sided 95% CIs using Greenwood's formula, provided the minimum follow-up in patients exceeds the time point to support stable estimation of the rate. The hazard ratio and corresponding 95% CI will be estimated using a Cox proportional hazards model including a factor for randomized arm and stratification factors of pre-transplant MRD status (MRD⁺ vs. MRD⁻/Unknown) and cytogenetic risk (Unfavorable vs. Other). The treatment effect on RFS will be evaluated using a stratified log-rank test. The significance level to be used in the RFS analysis at the final analysis will be based on $\alpha=0.05$ (two-sided).

As noted in Section 7.4.2, if an imbalance of more than 20% between the MT-401 and SOC arms is observed among the age, genetic mutations, transplant donor type, conditioning regimen, or complete remission status prior to transplant, the primary analysis may be modified to stratify for these factors.

A landmark analysis will be performed including only patients who are relapse free, alive and have not withdrawn from the study by Day 0.

Phase 2 Active Disease (Group 2):

The CR rate and the corresponding 95% exact CI will be calculated. The number and percentages of patients in each best disease response category per ELN recommendations will also be presented. Results will be presented separately for Subgroups C and D. Data from a matched synthetic control arm may also be obtained and compared against the CR rate from Group 2 active disease patients as part of a separate statistical analysis plan.

The DOCR will be estimated using the KM product limit method and summarized similar to RFS as described above.

7.4.5 *Secondary Endpoint Analysis Methods*

Safety Lead-in (Cohorts I and II) and Cohorts III-V:

CR and DOCR will be summarized descriptively for active disease patients in the Safety Lead-in (Cohorts I and II) and Cohorts III-V similar to Group 2. Summaries will be presented by cohort and overall.

Phase 2 Adjuvant (Group 1):

The statistical methods for analyzing OS and GRFS for Group 1 patients are identical to those described for RFS.

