The primary endpoint of RFS for Group 1 will be tested at $\alpha = 0.05$ (two-sided) at the final analysis. The analysis of RFS at the interim analysis will be performed for the purposes of testing for futility and possible re-estimation of sample size as described in [Section 7.4.7.3](#). Analysis at the interim and final analysis will be performed based on ([Chen et al. 2004](#)) in order to maintain the type 1 error at $\alpha = 0.05$ for RFS at the final analysis.

Secondary endpoints for Group 1, OS and GRFS, will be presented for descriptive purposes only and no adjustments will be made for multiplicity.

The primary endpoint of CR for Group 2 will be tested at $\alpha = 0.05$ (two-sided) at the final analysis. DOCR will be presented for descriptive purposes only and no adjustments will be made for multiplicity.

7.4.7.6 *Use of an “Efficacy Subset” of Patients*

The primary efficacy analysis for Group 1 will be performed on all randomized patients and the PP population will be utilized as a sensitivity analysis. The PP population will exclude patients received less than two-thirds of total planned dose or had other major protocol deviations.

7.4.7.7 *Examination of Subgroups*

Subgroup analyses may be conducted based on, but not limited to, the covariates defined in [Section 7.4.7.1](#).

For time to event endpoints forest plots of the event-free rates at landmark times may be generated to display the outcomes in subgroups. Additionally, Kaplan-Meier plots with subgroup KM curves overlaid on the same plot may be presented. For binary endpoints, the rates within subgroups may be presented in forest plots.

7.5 **Safety Evaluation**

Safety analysis will be carried out for the all treated patients population, to include all patients who receive at least one dose of study drug. Patients who do not complete the study, for whatever reason, will have all available data up until the time of termination included in the analysis. For safety analysis presented by study visit, the baseline value will be defined as the last value reported prior to first study drug administration.

7.5.1 *Extent of Exposure*

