7.6 Determination of Sample Size

Approximately 6-12 patients are expected to be enrolled in the Safety Lead-in portion of this study per a standard 3+3 design with 2 planned cohorts. In addition, approximately 9-18 patients (3-6 patients per cohort) are expected to be treated in the Cohorts III-V portion of this study as per a standard 3+3 design.

A total of 150 Group 1 patients will be randomized with a 1:1 allocation to receive MT-401 or to be under observation (SOC arm). Median RFS for the SOC arm is expected to be approximately 8 months. A clinically meaningful increase in median RFS for the MT-401 arm over SOC is thought to be 2 months or more. The primary analysis will be conducted when 90 RFS events have been observed. Ninety (90) RFS events provides 80% power with alpha=0.05 (two-sided) to detect a median RFS improvement of 6.5 months over the assumed SOC median RFS of 8 months (hazard ratio=0.55). Ninety RFS will be observed assuming uniform accrual of 150 patients (75 per arm) over a 50-month period and an additional 12 month minimum follow-up period. The DMC and Sponsor will review data from Phase 2 based on the planned interim analyses described in [Section 7.4.7.3](#).

If the decision is made to dose patients in Phase 2 with any of the MT-401 dosing regimens evaluated in Cohorts III-V, enrollment will continue in Phase 2 Group 1 to achieve 150 evaluable patients randomized and approximately 75 patients treated with the final MT-401 dose and the intended manufacturing process, thereby replacing any patients that have not been treated with the final Phase 2 product, as determined by the Sponsor.

A total of approximately 60 Group 2 patients are planned to be enrolled and treated with MT-401, 30 patients in Subgroup C (frank relapse patients) and 30 patients in Subgroup D (MRD⁺). After approximately 10 patients in each subgroup have progressed or had the opportunity to be followed for 6 months, clinical safety and efficacy will be reviewed comprehensively. Patients who develop CR_{MRD-} after bridging therapy and patients who relapse early (defined as less than 90 days ± 10 days and termed Group 2 Early Relapse patients) will be analyzed separately, and not be counted as part of the 60 patients in Group 2.

The sample size of 30 per subgroup is not based on a formal power calculation. An increase in the CR rate of greater than 10-15% compared to historical rates for standard of care would be considered clinically meaningful.

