If the decision is made to dose patients in Phase 2 with any of the MT-401 dosing regimens evaluated in Cohorts III-V, enrollment will continue in Phase 2 Group 2 to achieve 60 evaluable patients treated with the final MT-401 dose and manufacturing process, thereby replacing any patients that have not been treated with the final Phase 2 product as determined by the Sponsor.

For historical control response rates ranging from 5% to 40%, the observed treatment effects (and associated 95% confidence intervals) needed to attain 80% and 90% power with a sample size of 30 per subgroup are provided in [Table 3](#).

Table 3. Power^a and 95% Confidence Intervals Relative to Historical Control Rates

Historical Control CR Rate	Observed Treatment Effect (80% Power) (95% CI)	Observed Treatment Effect (90% Power) (95% CI)
5%	21% (9%, 40%)	25% (11%, 44%)
10%	29% (14%, 48%)	32% (17%, 52%)
15%	36% (19%, 55%)	40% (22%, 59%)
20%	43% (25%, 62%)	47% (28%, 66%)
25%	50% (31%, 68%)	53% (34%, 72%)
30%	53% (34%, 71%)	57% (37%, 75%)
35%	60% (40%, 77%)	63% (44%, 80%)
40%	63% (43%, 79%)	66% (47%, 82%)

^a based on a 1-sided exact test at the 0.05 alpha level.

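### Group 2 CR is to be tested two-sided at 0.05, but the only power table is for a one-sided 0.05 exact test, so its 80% and 90% figures are too high in three to six of eight rows

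*SAP*

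**What the plan says.** SAP 7.4.7.5 (Multiple Comparisons/Multiplicity): "The primary endpoint of CR for Group 2 will be tested at" alpha 0.05, and the sentence continues "two-sided) at the final analysis. DOCR will be presented for descriptive purposes only". This agrees with the general rule in SAP 7.1.1: "Statistical significance testing will be two-sided and performed using" alpha 0.05.

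SAP 7.6 plans "30 patients in Subgroup C (frank relapse patients) and 30 patients in Subgroup D". SAP Table 3 then lists, for historical CR rates from 5% to 40%, the rates that give 80% and 90% power with 30 patients. Its footnote reads "based on a 1-sided exact test at the 0.05 alpha level". Protocol 9.1.2, Table 7, has the same entries and the same footnote.

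For the analysis itself, SAP 7.4.4 says "The CR rate and the corresponding 95% exact CI will be calculated". It names no test and no null rate. Protocol 9.3.3 likewise plans the rate and the exact interval, and it adds: "Any comparison of Group 2 data to results from the retrospective study will be described in a separate SAP".

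On the status of the table, SAP 7.6 says "The sample size of 30 per subgroup is not based on a formal power calculation". Protocol 9.1.2 says the same.

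**The concern.** CR rate is a primary endpoint in Group 2. The sentence that plans its test and the table that gives its power use different rejection rules. A one-sided test at 0.05 allows up to 0.05 in the upper tail. An equal-tailed two-sided test at 0.05 allows 0.025. With only 30 patients, that difference can move the cutoff by a whole responder.

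Two things follow. The printed 80% and 90% figures may not hold for the planned test. A borderline result may also be read two ways: 7 of 30 against a 10% null is significant under the table's test, yet the 95% exact interval planned in SAP 7.4.4 still includes 10%. Because the SAP fixes neither the exact test nor the null, such a case could be settled only after the data are seen.

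**Working it through.** **Inputs.** n = 30 per subgroup (SAP 7.6). Null rates p0 = 5, 10, 15, 20, 25, 30, 35, 40%, with the printed 80% and 90% power rates p1 (SAP Table 3). One-sided 0.05 (table footnote). Two-sided 0.05 (SAP 7.4.7.5).

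**Formulas.** X is binomial(30, p).
- One-sided cutoff r: the smallest r with P(X ≥ r | p0) ≤ 0.05.
- Equal-tailed two-sided cutoff: the smallest r with 2 × P(X ≥ r | p0) ≤ 0.05, that is, an upper tail of at most 0.025. This test agrees with the Clopper-Pearson 95% interval.
- Minimum-likelihood two-sided p-value: the sum of P(X = x | p0) over all x no more likely than the observed count.
- Power: the probability of the rejection region at p1. In practice this is P(X ≥ r | p1).

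**Step 1: cutoffs under the table's own test, and what the two-sided tests make of them.**

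| p0 | One-sided r | Upper tail | Doubled | Min.-lik. p | 95% exact lower limit at r | Equal-tailed r | Min.-lik. r |
|---|---|---|---|---|---|---|---|
| 5% | 5 | 0.0156 | 0.0312 | 0.0156 | 5.64% | 5 | 5 |
| 10% | 7 | 0.0258 | 0.0516 | 0.0258 | 9.93% | 8 | 7 |
| 15% | 9 | 0.0278 | 0.0556 | 0.0354 | 14.73% | 10 | 9 |
| 20% | 11 | 0.0256 | 0.0512 | 0.0361 | 19.93% | 12 | 11 |
| 25% | 13 | 0.0216 | 0.0432 | 0.0322 | 25.46% | 13 | 13 |
| 30% | 14 | 0.0401 | 0.0802 | 0.0702 | 28.34% | 15 | 15 |
| 35% | 16 | 0.0301 | 0.0602 | 0.0533 | 34.33% | 17 | 17 |
| 40% | 17 | 0.0481 | 0.0962 | 0.0916 | 37.43% | 18 | 18 |

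The doubled value exceeds 0.05 in six rows, and in the same six rows the lower 95% limit lies below the null. The minimum-likelihood p-value exceeds 0.05 in three rows.

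**Step 2: power (%) at the printed rates.**

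| p0 | Printed 80% rate | One-sided | Equal-tailed | Min.-lik. | Printed 90% rate | One-sided | Equal-tailed | Min.-lik. |
|---|---|---|---|---|---|---|---|---|
| 5% | 21% | 78.5 | 78.5 | 78.5 | 25% | 90.2 | 90.2 | 90.2 |
| 10% | 29% | 81.0 | 67.7 | 81.0 | 32% | 89.0 | 79.2 | 89.0 |
| 15% | 36% | 80.8 | 68.4 | 80.8 | 40% | 90.6 | 82.4 | 90.6 |
| 20% | 43% | 81.1 | 69.5 | 81.1 | 47% | 90.7 | 82.9 | 90.7 |
| 25% | 50% | 81.9 | 81.9 | 81.9 | 53% | 89.3 | 89.3 | 89.3 |
| 30% | 53% | 81.0 | 69.6 | 69.6 | 57% | 90.7 | 83.1 | 83.1 |
| 35% | 60% | 82.5 | 71.5 | 71.5 | 63% | 89.9 | 81.9 | 81.9 |
| 40% | 63% | 81.9 | 70.6 | 70.6 | 66% | 89.7 | 81.3 | 81.3 |

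The one-sided columns reproduce the table: 78.5 to 82.5% where it says 80%, and 89.0 to 90.7% where it says 90%. The footnote is therefore accurate. The match is not exact to the last digit. The rates that give exactly 80% one-sided power are 49.4, 59.2 and 62.4% for nulls of 25, 35 and 40%, where the table prints 50, 60 and 63%.

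In the six rows affected under the equal-tailed test, power is 80 − 71.5 = 8.5 to 80 − 67.7 = 12.3 points below the stated 80%. It is 90 − 83.1 = 6.9 to 90 − 79.2 = 10.8 points below the stated 90%. A third two-sided exact test, Blaker's, gives the same cutoffs and powers as minimum-likelihood.

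**Step 3: rates that give the stated power with the equal-tailed test.** For the nulls in order: 21, 32, 39, 46, 49, 56, 62, 66% for 80% power, and 25, 36, 43, 50, 53, 60, 66, 69% for 90% power.

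**The case against.** The table states its own one-sided basis and is right on that basis. One can therefore call this an inconsistency between sections and not an arithmetic error. The SAP's analysis sections say two-sided throughout, so on sidedness alone the test sentence governs and the table is a planning illustration. The sample size is expressly not power-based, the Group 2 objective is to estimate, and no stopping rule uses the table. The size of the discrepancy also depends on a test the SAP does not name: under minimum-likelihood the 10, 15 and 20% rows are unaffected. In the 7 of 30 example the interval misses excluding the null by only 0.07 points (10 − 9.93).

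Most of this is fair and limits the weight of the point. It does not remove it. Both documents still print 80% and 90% power for a primary endpoint that the SAP says it will test, and at least three rows are wrong for that test under each of the two-sided exact tests examined. If estimation is all that is meant, the test sentence should not be there. The separate SAP for the retrospective or synthetic control does not fill the gap. Protocol 9.3.3 ties the retrospective study to Subgroup C, SAP 6.1 limits the synthetic control to Group 2C, and neither gives a null for the test in SAP 7.4.7.5 or for Subgroup D.

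**Conclusion.** The planned test and the power table do not match. The stated power is too high in six of eight rows if the two-sided test is equal-tailed, and in three (nulls 30, 35 and 40%) if it is minimum-likelihood. The 5% and 25% rows are unchanged under either.

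The six-row reading assumes that the planned exact interval is Clopper-Pearson and that the test is meant to agree with it. The SAP says only that the interval is exact, though the table's own intervals are consistent with Clopper-Pearson. The conclusion concerns the stated power and the missing test definition. It does not show that 30 patients per subgroup is inadequate. The point should be corrected, and it is not critical to the trial.

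**What to change.** Use one alpha, one sidedness and one named exact test in SAP 7.4.7.5, SAP Table 3 and Protocol Table 7. There are three ways to do this:

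1. **Preferred if a test is kept.** State the equal-tailed exact binomial test at two-sided 0.05 (0.025 per tail), which matches the 95% exact interval. Replace the table's rates with those in Step 3 of the working and recompute the intervals beside them. In the six affected rows the detectable rates move up by 2 to 4 points, mostly 3. In the 25% row, 49% replaces 50% through rounding only.
2. State one-sided 0.05 in SAP 7.4.7.5, note the exception to SAP 7.1.1, report matching 90% intervals, and keep the table.
3. Delete the test sentence and report the exact interval as estimation. This fits the Group 2 objective and costs only the formal significance claim. The power table should then go or be marked as illustrative.

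If a test is kept, fix one null CR rate for each subgroup before Group 2 data are reviewed.

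A smaller labelling point: the columns headed as observed effects hold assumed true CR rates, and the observed rate that rejects is lower. Against 10%, the equal-tailed test rejects at 8/30 = 27%, where the table shows 29%. Rename the columns and add the minimum number of responders that rejects (equal-tailed: 5, 8, 10, 12, 13, 15, 17, 18 of 30).

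The cost is one table in each document and one or two SAP sentences, with no extra patients.

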7.5.5 Vital Signs, Physical Findings, and Other Observations Related to Safety

7.5.5.1 Vital Signs

Vital sign parameter measurements will be summarized by study phase and cohort or treatment group. Descriptive statistics will be presented for results and change from baseline at each visit where parameters were scheduled to be collected.

7.5.5.2 Physical Examination

Results of the physical examination will be presented in patient data listings by study phase, patient, study visit, and body system.

7.5.5.3 GVHD Assessments

Shift from baseline in maximum overall grade for chronic GVHD will be summarized at each post-baseline visit and worst case post-baseline, and will include the count and percentage of patients within each shift category and treatment group.

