c Intervention Period includes study treatment and Active Follow-up and Survival Follow-up as defined in Section 4.4 (including for Safety Lead-in portion of the study). Day 0/Week 0 is considered the day of the first infusion of MT-401 (which differs from the Day 1 used for allogeneic HSCT). Each infusion and visit must be at least 2 weeks apart. Active Follow-up Period as defined in Section 4.4: occurs after the last dose of MT-401 has been administered until patient relapses/progresses or declines additional study visits. Timing of Follow-up Visits are in relation to the timing of the Day 0 visit. Sponsor will schedule Day 0 timing for all patients in all groups, including Group 1 SoC arm.

d SoC patients do not need to perform visit Weeks 2 or 4, unless clinically indicated. Week 0 visit for SoC patients may occur between days 85-130 post-HSCT, as instructed by Sponsor.

^e Survival follow-up begins after relapse/progression or active follow-up is completed and occurs every 3 months for 3 years, every 6 months for the remainder of the study (which can be phone contact to collect patient survival status [if alive, last date known alive, and if dead, date of death], and collect any additional anticancer therapy post-MT-401 or SoC received during study.

Confidential Page 19 of 74

f Brief physical exam, to include at a minimum, assessments of the Cardiovascular, Respiratory, and Gastrointestinal systems (height and weight will be needed at screening at minimum and any changes recorded if >10%).

g Pregnancy testing is required unless a patient has no possibility of being pregnant (for example post-hysterectomy). Perform as clinically indicated during intervention period for WOCBP. See Section 8.3.5 for details.

^h On day of MT-401 administration, laboratory assessments and/or disease assessments are completed prior to infusion (see Section 8.2.3 for additional details of laboratory assessments to be performed).

¹ Vital signs obtained within 1 hour pre- and post-infusion (window ± 15 min).

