4.4. Study Period and End of Study Definitions

Screening: begins when the informed consent form (ICF) is first signed. The patient is enrolled once Screening tests have been completed successfully and prior to HSCT for Group 1 patients, and prior to the start of manufacturing for Group 2 patients.

Baseline: A re-assessment of eligibility will occur within 14 days prior to group assignment for Group 1 to confirm eligibility has been met.

Randomization: Randomization to MT-401 or SoC for patients in Group 1 will occur once eligibility has been reconfirmed post-HSCT and groups have been assigned.

Study Period: begins the day of the first patient's first dose of MT-401 and ends at End of Study.

Confidential Page 32 of 74

- Study Treatment Period: begins with the day of the patient's first study treatment and ends the day the patient and investigator agree that the patient will discontinue study treatment or after all doses of MT-401 have been administered (whichever is earlier) (including for the Safety Lead-in portion of the study).
- Follow-up Period: begins the day after the study treatment period ends and is complete the day of the patient's death, withdrawal of consent, loss-to-follow-up or End of Study (whichever is earlier). It includes safety follow-up visits and additional long-term follow-up visits, as outlined in the SoA (Table 1):
 - Active Follow-up: occurs after the last dose of MT-401 has been administered until
 patient relapses/progresses or declines any additional study visits (but patient may
 continue with survival follow-up).
 - Survival Follow-up: begins the day a patient relapses as determined by investigator or declines any additional study visits and ends with the End of Study.

End of Study: A patient is considered to have completed the study if he/she has completed the planned study treatment and follow-up periods of the study as per SoA, withdrawn, patient's death or lost to follow-up.

No intervention following the End of Study is planned, and patients will return to their physician for further management.

4.5. 3+3 Design (Safety Lead-in and Cohorts III-V)

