6.4.1.2 Primary Efficacy Variables

Phase 2 Adjuvant (Group 1):

- RFS: defined as the time between the date of randomization and the date of first relapse per ELN recommendations or death by any cause, whichever occurs first. Relapse includes either hematologic and/or molecular relapse as defined in [Table 2](#) at any disease assessment. In the event that no relapse or death is documented prior to analysis cutoff or the start of new anti-cancer therapy, RFS will be censored on the date of the last evaluable disease assessment demonstrating no relapse prior to analysis cutoff or the start of new therapy. For patients who remain alive and have no baseline disease assessment or have no post-randomization disease assessment, RFS will be censored on the date of randomization. In addition, if relapse or death occurs after extended time without disease assessments, RFS will be censored on the date of the last evaluable disease assessment prior to the missed disease assessments.

For patients with relapse or death, a variable will be created to flag whether the earlier date of relapse or death occurs after extended time without disease assessments. The extended time is defined as below:

- Time from randomization date to Day 0 visit + 12 weeks + assessment window of 2 weeks, if the latest assessment prior to the event (relapse or death, whichever is earlier) \leq randomization date + 0.5*time from randomization date to Day 0 visit. For patients without Day 0 visit, an artificial Day 0 visit will be derived as randomization date + mean time from randomization date to Day 0 visit date in MT-401 arm, for analysis purpose only.
- 24 weeks + assessment window of 2 weeks, if the latest assessment prior to the event (relapse or death, whichever is earlier) \leq Day 0 visit + 6 weeks & $>$ randomization date + 0.5*time from randomization date to Day 0 visit
- 38 weeks + assessment window of 5 weeks, if the latest assessment prior to the event (relapse or death, whichever is earlier) \leq Day 0 visit + 18 weeks & $>$ Day 0 visit + 6 weeks
- 78 weeks + assessment window of 5 weeks, if the latest assessment prior to the event (relapse or death, whichever is earlier) \leq Day 0 visit + 37 weeks & $>$ Day 0 visit + 18 weeks
- 104 weeks + assessment window of 5 weeks, if the latest assessment prior to the event (relapse or death, whichever is earlier) \leq Day 0 visit + 78 weeks & $>$ Day 0 visit + 37 weeks

Phase 2 Active Disease (Group 2):

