- Baseline: the last available measurement prior to the first dose of MT-401 for patients enrolled in Cohorts I-V or Group 2. For patients randomized in Group 1, baseline for efficacy endpoints will be the last available measurement on or before the date of randomization. For patients randomized in Group 1, baseline for safety endpoints will be the last available measurement prior to the first dose of MT-401 for patients randomized to MT-401 and the last available measurement on or before the date of randomization for patients randomized to SOC.
- Potential follow-up time: data cutoff date – date of first dose of MT-401 (or date of randomization for Group 1 patients) + 1

- Study Day 0: the date of first dose of MT-401 (or date of randomization for Group 1 patients)
- Treatment emergent adverse events (TEAEs): Adverse events (AEs) with onset after the first dose of MT-401 or existing events that worsened after the first dose of MT-401 during the study. For the Group 1 SOC arm, TEAEs include AEs with onset after randomization or existing events that worsened after randomization.

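### The Group 1 worst-case chronic GVHD row compares crude percentages over observation windows that differ by arm, so it can show a difference at equal GVHD hazard

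*SAP*

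**What the plan says.** SAP 7.5.5.3 specifies the chronic GVHD display: "Shift from baseline in maximum overall grade for chronic GVHD will be summarized at each post-baseline visit and worst case post-baseline", with a count and percentage for each shift category and treatment group. Under SAP 7.1.1 the denominator is patients with available data. No person-time, cumulative incidence or common time window is planned for GVHD alone.

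**When assessment ends.** Protocol 1.3 places GVHD assessments at the scheduled visits. Its footnote on periods says that active follow-up "occurs after the last dose of MT-401 has been administered until patient relapses/progresses or declines additional study visits". Under Protocol 4.4, survival follow-up "begins the day a patient relapses as determined by investigator", and that contact is one "which can be phone contact to collect patient survival status". No GVHD assessment is listed for it.

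**When the window opens.** SAP 7.1.5 sets the Group 1 safety baseline at the last value before first dose for MT-401, but at "the last available measurement on or before the date of randomization for patients randomized to SOC".

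**Crossover.** Arm B patients who relapse may enter Group 2. They sign consent again (Protocol 10.2) and their visits restart (Protocol 1.3). SAP 7.1.1 bases safety outputs on the treatment actually received. No sentence says in which column their later GVHD is counted.

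**Nearest alternatives.** GRFS (SAP 6.4.1.3) combines severe acute GVHD, or chronic GVHD needing systemic treatment, with relapse and death. After Week 12, adverse event collection is limited to treatment-related events (Protocol 1.3 and 8.3.1).

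**The concern.** The probability of ever recording a worsened grade rises with the time during which someone looks. In this row the looking normally stops at relapse, which is a component of the primary endpoint. If MT-401 delays relapse, its patients are examined for longer and more GVHD is found at the same underlying hazard. The baseline rule works in the opposite direction: SoC patients are counted from randomization, MT-401 patients only from first dose. If chronic GVHD tends to appear early, that head start matters.

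GVHD is a named potential toxicity of allogeneic T cells (Protocol 8.2.1), and readers will compare the two columns. Neither GRFS nor the later adverse event tables isolate chronic GVHD by arm. What is at stake is a misreading of safety, in either direction. No hypothesis test is involved.

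**Working it through.** **Inputs from the documents (SAP 7.6, Protocol 9.1.1).** Median RFS 8 months on SoC and 14.5 on MT-401; 150 patients randomized 1:1 with uniform accrual over 50 months. SAP 7.4.4 sets the timing: "The primary analysis of RFS will be performed when 90 RFS events have been observed".

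**Assumptions.** Exponential RFS; assessment stops at the RFS event or the data cut; GVHD is independent of relapse and has the same hazard g in both arms. The base case is a 30% risk at 12 months.

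**Step 1, the plan's own figure.** Events for 80% power at HR 0.55, two-sided 0.05: 4 × (1.960 + 0.842)² / (ln 0.55)² = 88. With 90 events the power is 80.9%. The stated 90 events and 80% are reproduced.

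**Step 2, date of the cut.** λ = ln 2/8 = 0.0866 (SoC) and ln 2/14.5 = 0.0478 (MT-401). Expected events per arm by month τ ≤ 50 are 1.5 × [τ − (1 − e^(−λτ))/λ]. At τ = 44.9 this gives 50.4 + 39.6 = 90, with 75 × 44.89/50 = 67.3 patients accrued per arm.

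**Step 3, time under assessment.** The mean is (1/λ) × [1 − (1 − e^(−λτ))/(λτ)], which gives 12.3 months on MT-401 and 8.6 on SoC.

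**Step 4, the worst-case row at equal hazard.** g = −ln(0.70)/12 = 0.0297. With s = g + λ, the row is (g/s) × [1 − (1 − e^(−sτ))/(sτ)].
- MT-401: 0.383 × 0.722 = 27.7%
- SoC: 0.255 × 0.810 = 20.7%

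The gap is 7.0 points, or 18.6 against 13.9 patients. Its standard error is √(0.277 × 0.723/67.3 + 0.207 × 0.793/67.3) = 7.4 points.

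**Step 5, other assumptions, all with equal hazard.**

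| Scenario | MT-401 vs SoC | Ratio |
|---|---|---|
| Constant hazard, 10% risk | 9.9% vs 7.1% | 1.40 |
| Constant hazard, 50% risk | 43.3% vs 33.8% | 1.28 |
| 30% risk, detection only at visits (simulated) | about 25% vs 19-20% | |
| 30% risk, RFS gain of 2 months (cut at month 42.5) | 23.0% vs 20.4% | 1.13 |
| Onset only in first 6 months | | 1.10-1.11 |
| Onset only in first 3 months | | 1.05 |
| Constant hazard, 1-month gap from randomization to Day 0 | | 1.33 |
| First 6 months only, same 1-month gap | | 0.97 |
| First 3 months only, same 1-month gap | | 0.77 |
| GVHD after crossover counted as SoC, 25% of Arm B events cross over | | 1.18-1.23 |
| Same, 50% | | 1.06-1.14 |
| Same, 75% | | 0.96-1.06 |

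The last three rows assume a 2-month wait after the RFS event, then further assessment with a median of 4 or 8 months at the same g.

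**Step 6, candidate corrections.** A single rate per patient-month fails when onset is early. At equal hazard it gives 3.02 vs 4.02 per 100 patient-months with 3-month onset (ratio 0.75) and 2.64 vs 3.32 with 6-month onset (0.80), which understates GVHD on MT-401.

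A cause-specific hazard ratio does better but is not exact under visit-based detection. If the Week 2 and 4 assessments count, which SoC patients need not attend, simulation at equal hazard gives about 0.92-1.02 (constant hazard) and 1.06-1.15 (3-month onset), against crude ratios of 1.29-1.43 and 1.07-1.19. Restricted to visits scheduled in both arms plus any relapse visit, it gives about 0.91-1.03.

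Its precision is low. For a hazard ratio of 1.0 with 18.6 and 13.9 events, the 95% interval is exp(±1.96 × √(1/18.6 + 1/13.9)) = 0.50 to 2.00. With 10% risk (about 7 and 5 events) it is about 0.3 to 3.2.

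**The case against.** The strongest reply is that the direction is not fixed. A reader might infer from the RFS argument alone that the row will always make MT-401 look worse. The documents do not support that. The baseline rule is written into the SAP and, with early onset, turns the ratio below 1. The plan is silent on onset timing and does not assign GVHD after crossover. This objection stands, and the conclusion is limited accordingly.

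The end of assessment on SoC is also partly inferred. Active follow-up is defined from the last MT-401 dose, which Arm B never receives. Unscheduled visits follow the Week 24 assessments, so GVHD present at a relapse visit can be recorded, and Protocol 7.1 continues some safety collection after MT-401 stops. This is why assessment is said only to end normally at relapse. A relapse visit adds one look, not the later months.

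Readers have some protection: the by-visit rows are not inflated by this mechanism, the RFS curves show relapse-free time by arm, and SoC safety data are presented for reference only (Protocol 9.2). Crude worst-grade shift tables are also ordinary practice. That supports a minor rating, but it does not make the worst-case row comparable between arms.

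Finally, a reader might take the proposed hazard ratio as a full correction. It is not. With the MT-401-only visits left in and 3-month onset, it removes little of the distortion. The fix therefore restricts the visits and calls the result approximate.

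**Conclusion.** The point holds as a minor one. The worst-case row compares crude percentages over windows that close later on MT-401 if RFS is longer, and open earlier on SoC. At equal GVHD hazard it can show a difference unrelated to the product: about 25-28% against 19-21% under the design medians with a constant 30% 12-month risk. That is about 5 patients at the upper figures and within one standard error of zero. Early onset shrinks the gap. The baseline offset, or counting GVHD after crossover as SoC, can reverse it.

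No GVHD rate or onset pattern is given, so size and net direction are assumptions, as is independence of GVHD from relapse. What the documents do establish is that the windows are not aligned. A reader might go further and infer a threat to the RFS comparison or to type I error. Neither follows, because the table is descriptive and no test of GVHD is planned.

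**What to change.** Keep the shift table in SAP 7.5.5.3 and add the following for Group 1.

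1. Show months under GVHD assessment by arm beside the worst-case row.
2. Add a descriptive cause-specific hazard ratio with 95% CI for new or worsened chronic GVHD.
   - Start at the protocol's Day 0 visit in both arms. This is not the Study Day 0 of SAP 7.1.5, which is randomization for Group 1. Protocol 1.3 already provides for the visit: "Sponsor will schedule Day 0 timing for all patients in all groups, including Group 1 SoC arm". SAP 6.4.1.2 covers those without one: "For patients without Day 0 visit, an artificial Day 0 visit will be derived as randomization date" plus the mean interval in the MT-401 arm.
   - Count only visits scheduled in both arms (Weeks 12, 24, 52 and yearly) plus any relapse visit. Leave out the Week 2 and 4 assessments.
   - End at relapse, death, crossover or last GVHD assessment, whichever comes first.
3. State that GVHD after crossover is reported with Group 2.
4. State that the hazard ratio is approximate because detection is visit-based (about 0.91-1.03 at equal hazard in simulation) and that its interval will be wide (about 0.5 to 2.0).

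Do not use a single rate per patient-month as the correction. Cumulative incidence with relapse and death as competing events may be shown for absolute risk, but it does not remove the gap.

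The cost is some SAP wording and one descriptive table from assessments already scheduled, with no new visits. The drawback is low precision, which the table should state.
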